10.5.5.1 Handling of Solicited AE (eDiary) data

Solicited adverse events are recorded in the eDiary for 7 days post-vaccination (Day 0 to Day 7, Day 28 to Day 35, and Month 3 to Month 3 + 7 days [only applicable for booster participants]). All solicited AEs are considered causally related to the study treatment.

Solicited local symptoms including pain, induration (swelling), warmth, and erythema (redness), and solicited systemic symptoms including feverishness, chills, myalgia (muscle ache), fatigue (tiredness), headache, nausea, arthralgia (joint ache), and malaise (a general feeling of unwell) will be reported in a standardised manner over a period of 7 consecutive days after vaccination.

These solicited AEs and their intensity grades are based on the Food and Drug Administration (FDA) Guidance on Toxicity Grading Scale as described in Appendix 1 of the Protocol. If induration (swelling) or erythema (redness) are recorded as < 25mm in diameter in the eDiary, then this will be categorised as no event (grade 0) for the purpose of analysis. Derived intensity grades for induration and erythema are done based only on the numeric value of the parameter assessed, and clinical signs and symptoms will not be considered.

In addition, oral temperature will also be recorded for 7 days post-vaccination. Fever is defined as oral temperature $\geq 38^{\circ}\text{C}$ and the intensity grades are derived as specified in Appendix 1 of the Protocol.

Solicited AEs with missing intensity will not be included in the 'Any' count of the respective solicited AE.

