## **6.2 Treatment Day Assessments (Day 0, Day 28 and Month 3 [MVA-HBV Boost (UK participants only)])**

The following will be performed pre-vaccination:

- Re-check of eligibility criteria (Day 0 only)
- A urine pregnancy test will be performed
- Blood samples will be taken for haematology, biochemistry and LFTs
- A full physical examination will be performed
- Vital signs (pulse rate, blood pressure and temperature) will be measured
- A baseline assessment of local and systemic reactogenicity will be performed (see [Appendix 1](#))
- Blood samples will be taken for immunogenicity assessments and HBV disease markers

Participants will then receive study vaccine by intramuscular injection in the non-dominant arm, and will be observed for 30 minutes post vaccination for safety concerns. Nivolumab will then be administered via an infusion, if applicable, according to [Table 1](#). All participants will be assessed in the clinic for at least 30 minutes post-vaccination and post-nivolumab infusion in case of immediate adverse events. The first participant in each cohort will be observed for 1 hour. In the first cohort, the second participant will not be dosed until 48 hours after the first sentinel participant.

The following will be performed post-vaccination:

- The vaccination site will be covered with a sterile dressing during the observation period; it will then be removed and disposed of as GMO waste
- Vital signs (pulse rate, blood pressure and temperature) will be measured at the end of the observation period
- Local and systemic reactogenicity will be assessed at the end of the observation period
- On Day 0, an eDiary, tape measure and thermometer will be provided to perform self-assessment of local and systemic reactogenicity for 7 days after the vaccinations. Participants will be reminded to do the following daily for the 7 days after each vaccination:
  - Take and record their temperature
  - Measure and record the size of vaccination site redness
  - Assess the other solicited adverse events listed in the eDiary

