##### *7.4.1.1 Solicited Adverse Events*

Solicited adverse events are events the participant is specifically asked about. These adverse events are commonly observed soon after receipt of vaccines and relate to local and systemic signs and symptoms. Solicited adverse events will be collected daily in the eDiary for 7 days post-vaccination.

For this study, solicited adverse events to be collected include:

- Vaccination site reactions: pain, induration, warmth, erythema (redness)
- Systemic adverse events: feverishness, chills, myalgia, fatigue, headache, nausea, arthralgia, malaise

Participants will be asked to record the presence of these symptoms and grade the severity as described in [Section 8.2.4.1](#). Oral temperature will be measured using the thermometer provided and the diameter of induration will be measured with the tape measure provided.

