**A. Tables for Clinical Abnormalities**

Local Reaction to Injectable Product	Mild (Grade 1)	Moderate(Grade 2)	Severe (Grade 3)	Potentially Life Threatening (Grade 4)
Pain	Does not interfere with activity	Repeated use of non-narcotic pain reliever $\geq$ 24 hours or interferes with activity	Any use of narcotic pain reliever or prevents daily activity	Emergency room (ER) visit or hospitalization
Tenderness	Mild discomfort to touch	Discomfort with movement	Significant discomfort at rest	ER visit or hospitalization
Erythema/Redness *	2.5 – 5 cm	5.1 – 10 cm	$\geq$ 10 cm	Necrosis or exfoliative dermatitis
Induration/Swelling **	2.5 – 5 cm and does not interfere with activity	5.1 – 10 cm or interferes with activity	$\geq$ 10 cm or prevents daily activity	Necrosis

\* In addition to grading the measured local reaction at the greatest single diameter, the measurement should be recorded as a continuous variable.

\*\* Induration/Swelling should be evaluated and graded using the functional scale as well as the actual measurement.

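### The SAP grades eDiary induration by diameter alone, an undeclared departure from protocol Appendix 1 that may understate Grade 2–3 induration where no CRF record captures the effect on activity

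*SAP*

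**What the plan says.** SAP 10.5.5.1 bases the solicited events and their grades on the FDA "Guidance on Toxicity Grading Scale as described in Appendix 1 of the Protocol". It then sets two narrower rules for the diary:

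- "Derived intensity grades for induration and erythema are done based only on the numeric value of the parameter assessed"; clinical signs and symptoms are expressly left out.
- Induration or erythema values that "are recorded as < 25mm in diameter in the eDiary, then this will be categorised as no event (grade 0) for the purpose of analysis".

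Protocol Appendix 1 (Tables for Clinical Abnormalities) gives induration two criteria. Grade 1 needs 2.5–5 cm together with no interference with activity. Grade 2 is met by 5.1–10 cm or by interference. Grade 3 is met by at least 10 cm or by an effect that prevents daily activity. The footnote reads: "Induration/Swelling should be evaluated and graded using the functional scale as well as the actual measurement". Protocol 8.2.4.1 makes Appendix 1 the grading standard wherever possible.

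Two further SAP rules decide what reaches the tables. Section 10.5.5 combines eDiary and CRF data and uses the higher grade from either source. CRF induration keeps its own categories from none to life-threatening. Section 10.10 says that, where both sources have a record at the same date and time, the primary analysis uses the CRF record. SAP 6.1 lists the changes from the protocol, down to a change of plot type, but not this one.

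**The concern.** The SAP names a scale as its standard and then omits half of it for one symptom. The omitted half is joined to the other by an *or* at Grades 2 and 3, so leaving it out can only lower a diary grade, never raise it. Reactogenicity is part of the primary objective and of the first primary endpoint. If the tables show less Grade 2–3 induration than the protocol's scale would give, a reader who takes them to be graded on Appendix 1 has no signal that they are not.

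**Working it through.** No arithmetic in the plan underlies this rule, so the check sets the two grading rules side by side.

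**Step 1. Diary record only.** The inputs are the diameter cut-points and the functional criteria of Appendix 1, and the diameter-only rule of SAP 10.5.5.1. The Appendix 1 grade is the worse of the diameter grade and the functional grade. Exactly 10 cm, which appears under both Grade 2 and Grade 3, is taken as Grade 3. Grade 4 (necrosis) is outside the comparison.

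| Diameter | SAP diary grade, any function | Appendix 1, no interference | Appendix 1, interferes | Appendix 1, prevents daily activity |
|---|---|---|---|---|
| <2.5 cm | 0 | 0 | 2 | 3 |
| 2.5–5 cm | 1 | 1 | 2 | 3 |
| 5.1 to <10 cm | 2 | 2 | 2 | 3 |
| ≥10 cm | 3 | 3 | 3 | 3 |

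The rules agree when there is no interference and at 10 cm or more. They differ in five cells, and the SAP grade is lower in all five. The largest gap is three grades: 2 cm induration that prevents daily activity is Grade 3 under Appendix 1 and no event under the SAP.

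**Step 2. Add the CRF.** Under SAP 10.5.5 the tabulated grade is max(diary grade, CRF grade). If the CRF records the induration as severe in the same 7-day period, the result is max(0, 1, 2 or 3; 3) = 3 in every row, and nothing is lost. The understatement therefore needs a second condition: no CRF record carries the functional effect.

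**Step 3. When that can happen.** Protocol Table 2 places clinic reactogenicity assessments on the vaccination days and at the visit 7 days later. It also marks the Day 1 and Day 29 calls, but protocol 6.3.1 describes those calls only as reminders to complete the eDiary. The days in between rest mainly on the diary.

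**Step 4. How often.** This cannot be computed. The documents give neither a rate of activity-limiting induration nor the share that the CRF would capture. An illustration can borrow the sample-size statement (protocol 10.1, SAP 8.1) of an 80% chance of seeing an event of 10% incidence among 16 participants. That figure reproduces: 1 − 0.9^16 = 0.815. Now assume that Grade 3 induration has a true incidence of 10% and that a share c of cases is tabulated as Grade 3. The chance that a group of 16 shows at least one is 1 − (1 − 0.10c)^16:

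| c | Chance of at least one tabulated case |
|---|---|
| 1 | 81.5% |
| 0.75 | 71.3% |
| 0.5 | 56.0% |
| 0.25 | 33.3% |

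Both the 10% and c are assumptions. The table shows sensitivity and is not an estimate for this trial.

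**The case against.** The strongest reply is that the CRF is a real safeguard. The higher of the two sources is tabulated, CRF induration is not subject to the diameter rule, and protocol 8.2.2 tells participants to call in abnormalities between visits. This stands, and it makes the understatement conditional. It does not remove it for induration that limits activity and settles between visits.

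The second reply is that the Appendix 1 footnote is a recommendation, on pages marked as nonbinding, and that the protocol adopts the scale only where possible. The 25 mm cut-off also matches the scale's own lower bound of 2.5 cm. Both points are fair. But the SAP claims to follow that scale, so a departure from it should be declared.

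The third reply is that the functional data may not exist. Protocol 7.4.1.1 asks participants to grade severity and adds that "the diameter of induration will be measured with the tape measure provided", while SAP 10.5.5 routes induration away from the activity categories in its Table 5. The documents do not show whether the eDiary held a functional item for induration. This stands, so the remedy has to be conditional.

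A reader might also infer more than the documents support:

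- *That Grade 3 local reactogenicity in general is understated.* Pain and warmth use the activity categories of SAP Table 5, and Appendix 1 gives erythema no functional criterion at Grades 1–3. Only induration is affected.
- *That the group holding rule is weakened.* Protocol 3.1.3 rests on the Investigator's assessment, and nothing says that the rule uses SAP-derived diary grades.
- *That the measuring instructions conflict.* Protocol 6.2 says "Measure and record the size of vaccination site redness" and 7.4.1.1 names induration. Section 6.2 also asks for the other solicited events in the eDiary, so the two can be read as complementary.
- *That induration without a diameter is always lost.* The SAP says "Solicited AEs with missing intensity will not be included in the" count of any event, but a CRF grade or a graded diary record on another day would still count the participant.

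**Conclusion.** The point holds in a limited form. SAP 10.5.5.1 departs from the scale that it names for one symptom, in one data source and in one direction, and SAP 6.1 does not say so. Where the diary is the only source, induration that prevents daily activity loses three grades below 2.5 cm, two at 2.5–5 cm and one at 5.1 to <10 cm. Induration that interferes with activity loses two grades below 2.5 cm and one at 2.5–5 cm. Grade 2–3 induration may therefore be understated.

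This rests on the diary grade being derived exactly as written and on no CRF record in the same 7-day period carrying the functional effect. No effect on any particular table has been shown, and the frequency is unknown. The change is worth making because the endpoint is primary and the correction is small.

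**What to change.** - **If participants' functional severity for induration was recorded (protocol 7.4.1.1):** in SAP 10.5.5.1, derive the diary grade as the worse of the diameter grade and the functional grade, before taking the maximum with the CRF grade. Set diameters under 25 mm to Grade 0 only when no interference with activity is recorded.
- **If no functional item was collected:** list the departure in SAP 6.1, footnote the solicited adverse event tables to say that diary induration is graded by size only, and show CRF-graded induration separately.
- **In either case:** reconcile SAP 10.5.5 with 10.10. For records at the same date and time the first takes the higher grade and the second takes the CRF record, so they give different answers whenever the diary grade is higher. State which rule governs the primary analysis.

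Changing the diary instructions would not help. The SAP change history for version 1.2 says that no participant had the Month 3 boost, which implies that the Day 0 and Day 28 diary periods were already over.

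The cost is a few lines of SAP text and derivation code, or one declaration, a footnote and a separate CRF display. The downside is that reported induration severity may be slightly higher.

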10.5.5 Solicited AEs

For the Solicited AE analysis, data collected on both the eDiary (*Solicited Adverse Event*) and the CRF (*Local/Systemic Reactogenicity*) will be summarised together using the maximum reported intensity grade from either source.

Post-vaccine assessments on the day of the first vaccination and up to and including 7 days post-vaccination will be summarised under the First vaccination, and post-vaccine assessments on the day of

the second vaccination and up to and including 7 days post-vaccination will be summarised under the Second vaccination. This is the 7-day reactogenicity period. Pre-vaccine assessments for the first and second vaccination will not be included in the summaries and will be listed only.

The severity values will be mapped from the two sources as shown in Table 5. For erythema, induration, and fever, the eDiary values will be mapped to the intensity grades as described in Section 10.5.5.1.

Table 5 Solicited AE Severity

Severity	Solicited AE (eDiary) categories	Local/systemic reactogenicity (CRF) categories
Grade 0	0 – None	None
Grade 1	1 – No interference with activity	Mild
Grade 2	2 – Some interference with activity	Moderate
Grade 3	3 – Significant; prevents daily activity	Severe
Grade 4	4 – ER visit or hospitalisation	Life Threatening

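### A solicited reaction that is reported but never graded is left out of the 'Any' count while the participant usually stays in the denominator, so reactogenicity incidence can only be understated

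*SAP*

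**What the plan says.** The counting rule is in SAP 10.5.5.1: "Solicited AEs with missing intensity will not be included in the 'Any' count of the respective solicited AE". SAP 10.8 confirms that nothing is imputed except missing relatedness.

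SAP 12.7.2.2 tabulates each symptom after each vaccination and overall. The denominator is the participants who gave a severity for any solicited symptom on any day of the 7-day period, not those who gave one for the symptom in question.

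Grades come from two sources. SAP 10.5.5 says eDiary and CRF data "will be summarised together using the maximum reported intensity grade from either source". On the CRF, severity is a category from none to life-threatening (SAP Table 5) and needs no measurement. In the eDiary, SAP 10.5.5.1 says: "Derived intensity grades for induration and erythema are done based only on the numeric value of the parameter assessed". Induration or redness is Grade 0 only if it is "recorded as < 25mm in diameter in the eDiary, then this will be categorised as no event (grade 0) for the purpose of analysis".

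On collection, Protocol 7.4.1.1 says: "Participants will be asked to record the presence of these symptoms and grade the severity". It adds that "the diameter of induration will be measured with the tape measure provided". The daily reminders in Protocol 6.2 have a different item: "Measure and record the size of vaccination site redness". Protocol Appendix 1 gives diameter grades for both reactions and adds: "Induration/Swelling should be evaluated and graded using the functional scale as well as the actual measurement".

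**The concern.** The 'Any' row measures occurrence, and a reaction reported without a grade has still been reported. Removing it from the numerator alone records that participant as free of the symptom. Because the rule only ever removes events, it cannot average out.

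The most exposed entries are local reactions. If a participant notes redness or induration in the eDiary but enters no diameter, no eDiary grade can be derived. The two protocol instructions each name one of the two measurements, which makes a blank diameter easier to arrive at than it need be.

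At stake is the reactogenicity profile of a vaccine trial whose primary objective names reactogenicity, in groups small enough for one participant to move a rate visibly.

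**Working it through.** **The plan's own figure.** The documents give no figure for this rule. The nearest is the statement in SAP 8.1 and Protocol 10.1 that 16 participants give an 80% chance of seeing a severe or serious event of 10% incidence: 1 − 0.9^16 = 0.815, which agrees. The point does not depend on it.

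**Inputs.** Groups 2 and 3 are planned at 16 each (Protocol Table 1). Groups 1 and 4 closed at 10 and 9 (SAP 8.1). The 12.7.2.2 denominator may be smaller than the group, so these sizes are used as assumed denominators.

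**Step 1: what happens to one participant.** Suppose redness is reported on some days with no size entered, the CRF holds no redness grade, and pain is Grade 1.
- Pain: in the numerator and in the denominator.
- Redness: not in 'Any' (10.5.5.1), but in the denominator because pain has a severity (12.7.2.2).
- Had a size of 30 mm been entered, redness would be Grade 1 under Appendix 1 and would count.

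**Step 2: size per participant.** With x reporting a symptom and a denominator n, the rate falls from x/n to (x − 1)/n, a loss of 1/n.

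| Denominator | Loss per participant |
|---|---|
| 16 | 1/16 = 6.25 points |
| 10 | 1/10 = 10.0 points |
| 9 | 1/9 = 11.1 points |

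**Step 3: illustration.** Assume 8 of 16 report redness, 8/16 = 50%. With 1, 2 or 3 of them ungraded throughout, the SAP rule gives 7/16 = 43.8%, 6/16 = 37.5% or 5/16 = 31.3%. These counts are assumptions.

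**Step 4: direction.** If the participant has no severity for any symptom, he or she leaves the denominator too: 7/15 = 46.7%, still below 50%. In general (x − 1)/(n − 1) cannot exceed x/n, because x is at most n. Both routes lower the rate or, when x = n in the second, leave it unchanged.

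**Step 5: when an event is actually lost.** The count is per participant over the period, so one graded day from either source is enough. CRF reactogenicity is recorded after vaccination on the dosing day and at the visit 7 days later; Protocol Table 2 also marks the telephone call on Day 1 or 29. The loss therefore needs a reaction with no grade on any diary day and none at those contacts, which chiefly means one confined to the days between them. The 'overall' row loses it only if no grade exists after either vaccination.

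**Step 6: whether anything else restores it.** The sensitivity analysis in SAP 10.10 brings back duplicate records, not ungraded ones. The reaction remains in the listings (12.7.2.2), but no planned table shows how many were set aside.

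**The case against.** The strongest reply is that this is a pre-stated complete-case convention with an unknown and possibly zero effect. SAP Table 5 shows one eDiary item per symptom, running from none to Grade 4, so for most symptoms presence and grade may be one response and a missing intensity may simply be an unanswered item. The table concerned sits under other safety endpoints, is descriptive, and feeds no test. All of this stands and limits how much the rule can matter. It does not explain why a reported event should leave an occurrence count, and the rule itself presupposes that such records can exist.

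A reader might also infer more than the documents support:
- *That redness and induration are graded only from a measurement.* This is true of the eDiary grade alone. A CRF grade needs no diameter and, under SAP 10.5.5, can place the reaction in 'Any'.
- *That the protocol never asks for both measurements.* Section 7.4.1.1 refers to 8.2.4.1, which refers to Appendix 1, where both reactions have diameter grades. SAP 10.5.5.1 likewise expects a diameter for each in the eDiary. What stands is that neither participant-facing instruction names both.
- *That a blank diameter is recoded to Grade 0.* It is omitted. Grade 0 is for a recorded value below 25 mm, which for redness matches where Appendix 1 starts Grade 1. The non-event arises through the denominator.
- *That the SAP says ungraded unsolicited events still count.* SAP 10.5.1 says only that missing severity is not imputed, so it sets no contrary precedent.

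**Conclusion.** The point holds in a narrow form. A solicited reaction reported as present but graded in neither source during the 7-day period is excluded from 'Any' and, when any other symptom has a severity, is counted as a non-event. Incidence can be understated but not overstated by this rule.

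The size is 6.25, 10.0 or 11.1 points per affected participant for denominators of 16, 10 and 9. The total effect cannot be computed, because no rate of missing grades is given and the eDiary design is not described; if the eDiary forces a diameter and a grade, the effect is nil. The exposure is mainly redness and induration reported in the diary between CRF assessments. The change is worth making because it is cheap and removes a one-directional error; the documents do not show that any particular number of events will be lost.

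**What to change.** Replace the sentence in SAP 10.5.5.1 with: *Solicited AEs reported as present in either source but with no intensity grade are included in the Any count and shown in a Grade missing row of the severity table; unanswered items are not counted as events.*

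Match the denominator wording in SAP 12.7.2.2, so that a participant whose only report is ungraded is in the denominator as well as the numerator.

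In Protocol 6.2 and 7.4.1.1, name both measurements, redness and induration, in each place.

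The cost is one SAP sentence, a matching phrase, one table row and a wording alignment in the protocol. The SAP change needs no new data. If no such records exist, the row shows zero and confirms it.

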10.6 Treatment-Emergent Events

Treatment-emergent events are defined as those occurring during or after the first study vaccine administration.

